Systematic observations are carried out regarding treatment compliance in both control and intervention groups. In addition, an electroencephalography (EEG) examination is carried out at the baseline visit and after 12 months in 30 participants. After the 12-month visit, a qualitative study is conducted. This study will collect data by interviewing spouses of participants. After the end of the study, the utility of serum determinations of anti-dementia drugs in relation to side effects and clinical efficacy is assessed by comparing the scores of participants in the control and intervention groups for the aforementioned clinical scales.

Project initiator, sponsor, responsible physician and contact person:

[name], senior physician, MD, PhD

Department of Neurology Zealand University Hospital (SUH) [name]
[name] Denmark

Aims of the study

- Investigate whether determination of serum concentration, and regulation of the dose on the basis hereof, improve the clinical treatment response – including whether insufficient clinical effect could be due to too low a serum concentration
- Investigate whether early development of side effects during treatment with anti-dementia drugs is due to too high a serum concentration (ie. serum concentrations above the therapeutic reference range).
- Characterize the proportion of participants who reach a serum concentration within the recommended therapeutic reference range when treated with standard dosages of anti-dementia drugs.
- Study whether the recommended therapeutic reference ranges are valid in relation to clinical efficacy
- Investigate the relationship between serum concentrations and clinical efficacy in different stages of the dementia disease
- Investigate whether measurements of serum concentrations improve treatment compliance, both in relation to side effects and in relation to clinical efficacy
 - Investigate whether sex differences impact serum concentrations, which potentially may have an impact on optimal drug dosing.
 - Investigate whether genetic variation of the metabolism of anti-dementia drugs, impact serum concentration and thus potentially may be important for optimal dosing. With regards to this, analysis of the APOE genotype and analysis of the BchE-K/K variant will be carried out.
- Describe aspects of treatment compliance in in a Danish memory clinic

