- who give informed consent to participation.

Both patients with mild-moderate dementia and patients with moderate to severe dementia are enrolled, because we want to explore whether the correlation between effect and serum concentration varies depending on the stage of dementia.

Exclusion criteria for participants

- Patients not accompanied by relatives to study visits.
- Patients who live alone and do not have help with the medication administration
- Inability to cooperate to testing, also severely impaired vision or hearing, amputation or other severe disabilities.
- Inability to meaningfully give informed consent due to cognitive impairment.
- Patients with known underlying psychiatric illnesses (schizophrenia, bipolar affective disorder, etc.). Depression is permitted if the patient has been on regular medical treatment for at least 3 months prior to inclusion.
- Patients with known neurological conditions (MS, epilepsy, brain tumors etc.), which in themselves could be contributing to the patients cognitive symptoms.
- Patients with medical conditions (kidney, liver, metabolic etc.) which in themselves could be contributing to the patients cognitive symptoms.
- Patients who, currently or in the past 3 months before enrollment, have been treated with anti-psychotics or neuroleptics. Minimal doses of benzodiazepines or hypnotics are accepted.
- Patients with previous heavy abuse of alcohol or illegal drugs, or any abuse within the last 3 months before inclusion.

- Patients with previous severe head trauma or neuroinfections, which in themselves could contribute to the patients cognitive symptoms.
- Patients who have had ECT [Electro Convulsive Therapy] treatment within the last 3 months.
- General anesthesia within the last 3 months.

Withdrawal criteria for all

- The participant or relative wishes to withdraw from the study.
- Symptoms deemed unacceptable by the physician responsible for the trial in accordance with the above exclusion criteria.
- Medical reasons, including if the treatment is changed to an anti-dementia drug for which serum concentrations are not measured in this study [galantamin or rivastigmine].

Study execution and visits

Inclusion interview/recruitment

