Assessment of treatment compliance is carried out according to the memory clinic's general clinical practice. This consists of participants and especially their relatives being interviewed by a physician and contact nurse at follow-up visits about whether the medication has been ingested regularly during the previous treatment period. If the medication is not ingested regularly as prescribed, this is included in the clinical assessment of effect and possibly side effects, and noted in the medical record. In the context of the study, this practice will be followed, i.e. the assessment is carried out at the control visits after ½ and 1 year of treatment. It will also be noted in the CRF whether the drug is ingested either "completely regularly", "regularly with less than 10 missed daily doses in 6 months", "less regularly, with more than 30 missed daily doses in 6 months" or "irregularly with more than 60 missed daily doses in 6 months".

Endpoints for the prospective study

Primary endpoint

When a participant has attended the 1-year follow-up visit the study participation is completed for that individual. When the last participant (as based on the power calculation) has attended the 1-year follow-up visit quantitative data collection for the study will be complete.

Quantitative outcome variables explored in the study

- MMSE
- ACE
- DAD
- CGI
- NPI
- serum concentrations [of either Donepezil or Memantine]
- Genetic variants (liver enzymes, APOE, BchE-K/K)
- Sex
- comorbidity registration
- compliance registration
- EEG

Statistics and power calculation

Several studies and meta-analyses have shown that the clinical effect of anti-dementia drugs can be detected for at least one year after initiation of treatment (23). The effect generally consists of a delay in the development of symptoms corresponding to 2 points on an MMSE scale after one year. We define optimized clinical effect as a decrease of less than 2 points on the MMSE scale in one year. This means that all participants whose score decreases 2 or more points in a year have a sub-optimal clinical effect, while participants whose score has a decrease of less than 2 points in a year has optimal clinical effect. It is emphasized that, as in general clinical practice, emphasis is not placed solely on the change in MMSE score when the effect is assessed. The assessment is based on an overall clinical assessment, where the CGI score is deemed suitable.

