Based on clinical database information, 15-20 newly referred patients eligible for study participation will likely be referred to RVD per month. If it is assumed that approx. half will participate in the project, approx. 100 patients could be included in one year.

If it is assumed that <50% of the participants reach the recommended serum concentration and thus relevant clinical effect on standard dosing (cf. pilot study), and that this can be increased to 75% by dose adjustment after S concentration determination, the following calculation can be performed on the basis of the formula:

$$N > (Z_{2\alpha} + Z_{\beta})^2 \times (P_1(1-P_1) + P_2(1-P_2)) / (P_1 - P_2)^2$$

where N is the number of necessary participants in each group, α is significance level 5%, β is the probability of type 2 error (strength is $1-\beta = 80\%$), P_1 is dose optimization (optimized clinical effect) with regular dosing, P_2 is dose optimization (optimized clinical effect) guided by S-level and possibly side effects.

$$N > (1.96+0.84)^2 \times (0.5 \times 0.5 + 0.75 \times 0.25) / 0.25^2 = 7.84 \times (0.25 + 0.1875) / 0.0625 \sim 55$$

In other words, 110 participants must be included in the project period in order to calculate the clinical utility of serum concentration measurements with the stated assumptions. Realistically this goal for participant recruitment can be reached within a study period of one to two years.

Risk assessment (risks and discomfort)

Blood test

For all participants in the study a single blood sample is collected for genetic analyses. For the intervention group, as stated, a single blood sample is also taken in case of side effects, and after $\frac{1}{2}$ and 1 year. The blood sample is collected in a completely routine manner by a trained professional. The procedure is not associated with any other discomfort or inconvenience, apart from what is known for a routine blood test in a normal clinical context. For the control group, a blood sample is collected at the 1 year follow-up visit, when the CRF is closed for that participant.

MMSE, ACE, GDS, DAD, NPI

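### The 2-point MMSE rule on which the trial is sized does not identify drug benefit in a participant, and comparing the arms on it would cost about 36-37% of the information in MMSE change

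*Combined protocol and SAP*

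**What the plan says.** In 'Statistics and power calculation' the plan first describes what the drugs do: "The effect generally consists of a delay in the development of symptoms corresponding to 2 points on an MMSE scale after one year". The next sentence sets the response criterion: "We define optimized clinical effect as a decrease of less than 2 points on the MMSE scale in one year". The one after applies it to individuals: "all participants whose score decreases 2 or more points in a year have a sub-optimal clinical effect".

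The sample-size paragraph follows. Its assumption reads "If it is assumed that <50% of the participants reach the recommended serum concentration and thus relevant clinical effect on standard dosing", and further "that this can be increased to 75% by dose adjustment after S concentration determination". In the legend to the formula, P1 and P2 are the proportions with optimized clinical effect under regular and serum-guided dosing. The trial is therefore sized on the dichotomy.

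Other text points elsewhere:

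- Directly after the rule, the plan says that "emphasis is not placed solely on the change in MMSE score when the effect is assessed" and calls the CGI score suitable for an overall assessment. The CGI description under 'Methods and materials' likewise gives that scale weight in judging treatment response. Neither place gives a CGI threshold or a rule for combining it with the MMSE.
- The Introduction says that utility will be assessed "by comparing the scores of participants in the control and intervention groups for the aforementioned clinical scales".
- MMSE is listed among the quantitative outcome variables.
- The paragraph headed 'Primary endpoint' describes completion of the 1-year visit and names no outcome variable. No statistical test is specified anywhere.

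The population is broad. AD, DLB and PDD are all eligible, and "Both patients with mild-moderate dementia and patients with moderate to severe dementia are enrolled".

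**The concern.** A delay of 2 points is a difference from the course that would have occurred without the effect. A limit of 2 points on a participant's own decline is a different quantity, and the text moves from one to the other without argument. A participant who would have lost 4 points and loses 2 has had exactly the cited effect, yet is classed as sub-optimal. A participant who would have been stable and loses 1 point has had no benefit, yet is classed as optimal. With one limit across three diagnoses and all stages, natural rate of decline enters the label directly.

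Two things are at stake. The first is interpretation: a responder percentage reported under this definition would be read as the share of participants whose treatment works well. The second is precision: a comparison of proportions uses less of the information in the two MMSE values than a comparison of the graded change.

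**Working it through.** **Inputs from the plan.** P1 = 0.50 (the text says below 50%), P2 = 0.75, two-sided 5% (z = 1.96), 80% power (z = 0.84), equal groups.

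**Step 1: the plan's own figure.** N = (1.96 + 0.84)² × (0.50 × 0.50 + 0.75 × 0.25) / 0.25² = 7.84 × 0.4375 / 0.0625 = 54.88, so 55 per arm and 110 in total. The stated figure reproduces. With a pooled-variance test, power at 55 per arm is 78%, so 'about 80%' is fair.

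**Step 2: the same contrast on the graded scale.** Assume normally distributed change with equal SD in both arms. Moving the proportion on one side of a fixed cut from 50% to 75% needs a shift of z(0.75) − z(0.50) = 0.674 SD.

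- Size for 80% power: n = 2 × ((1.960 + 0.842) / 0.674)² = 34.5, so 35 per arm (36 with a t-test).
- Information lost by dichotomising: 1 − 34.5 / 54.88 = 37%. With rounded sizes, 1 − 35 / 55 = 36%.
- Power at 55 per arm: Φ(0.674 × √(55/2) − 1.96) = Φ(1.58) = 94%. The t-test gives 93.9%.

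**Step 3: sensitivity of the loss.**

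| Setting | Information lost |
|---|---|
| Small effect, cut at the median (1 − 2/π) | 36% |
| Whole-point MMSE change, assumed SD 2.5 to 4, 50% vs 75% | 36-37% |
| P1 = 33% to 45%, P2 = 75% | 31-35% |
| Small effect, cut where 70% are below the limit | 42% |
| Small effect, cut where 80% are below the limit | 51% |

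**Step 4: how far the label departs from drug benefit.** The plan gives no mean decline or SD, so these are assumptions: untreated mean decline μ of 2 to 4 points, SD 2.5 to 4, normal, whole-point scores (so the cut lies at 1.5).

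- If every participant gains the full 2 points, the share still labelled sub-optimal is 1 − Φ((1.5 − (μ − 2)) / SD). At μ = 3 and SD = 3 this is 1 − Φ(0.17) = 43%; over the whole range it is 27% to 58%.
- If no participant gains anything, the share labelled optimal is Φ((1.5 − μ) / SD). At μ = 3 and SD = 3 this is Φ(−0.50) = 31%; over the range it is 16% to 45%.

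**Step 5: what the 50% and 75% stand for.** The control rate comes from attainment of the serum reference range (8 of 24 samples in the pilot, under 'Background'), which the plan equates with clinical effect. It is not MMSE data. At an assumed SD of 2.5 to 4, 0.674 SD equals 1.7 to 2.7 MMSE points, roughly the whole drug effect that the plan cites, to be gained from dose adjustment alone.

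**The case against.** The strongest reply is that no section says the arms will be compared on the responder proportion. The rule appears only in the power section. The Introduction speaks of comparing scores, the 'Recruitment' text assesses overall response on five scales, and MMSE is listed as a quantitative variable. This stands: the loss is certain only for the basis on which the trial was sized, and is conditional for the analysis. It also stands that the CGI is given a role, so the MMSE rule is not the plan's only statement about response. It is, however, the only one with a threshold.

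Three stronger readings are tempting and are not supported:

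- *The rule biases the trial.* Both arms share it, and randomisation balances natural decline, diagnosis and stage in expectation. Interpretation and precision suffer; the validity of the comparison does not.
- *Slow decliners will be counted as drug responders in the serum analyses.* 'Study design' says only that serum concentrations are correlated with clinical response. No text applies the 2-point label there.
- *The trial has 94% power, or needed only 35 or 36 per arm.* The rates behind these figures are serum-attainment assumptions, and recruitment ended in February 2022. The figures compare two analyses under one assumption and say nothing about the likely effect.

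A last objection also stands: graded change does not isolate drug benefit in an individual either, because there is no untreated arm.

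**Conclusion.** The point holds in a limited form. The plan turns a 2-point drug effect into a cut-off on each participant's own decline and sizes the trial on the result. The label cannot be read as drug benefit in a participant. If the arms are compared on it, about 36-37% of the information in MMSE change is lost, assuming normal change, equal SDs and the plan's 50% versus 75%; with a control rate of 33% to 45% the loss is 31-35%. The mislabelling ranges depend on assumed decline and SD and are illustrative. Whether the loss occurs depends on a choice of analysis that the documents leave open. This is a cheap improvement that should be made, not a flaw that invalidates the randomised comparison.

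**What to change.** In 'Statistics and power calculation':

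1. State that MMSE is compared between arms as a graded 12-month score, adjusted for baseline MMSE. Adjustment can add precision; the plan gives no correlation from which to size the gain.
2. Report a decrease of less than 2 points as supporting description only, and remove the statement that it separates optimal from sub-optimal drug effect in a participant.
3. Reconcile this with the CGI text in the same section and in the CGI description, so that the place of the CGI beside the MMSE is explicit.

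In the serum-efficacy analyses, use graded MMSE change adjusted for baseline MMSE and diagnosis, not the label. Add that, without an untreated arm, this recovers precision but still does not isolate individual drug benefit.

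The cost is wording: the MMSE is already measured before enrolment and at the 1-year visit. The downside is that a mean difference is less intuitive than a responder percentage, which is still reported.

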The anti-dementia drugs currently on the market (acetylcholinesterase inhibitors (ChEI) and memantine) do not have any documented disease-modifying effect in relation to the pathophysiology of AD as such, but only a symptomatic effect. When ChEI were introduced, analyzes of the optimal dosage level were carried out both in relation to safety and side effects, but also in relation to clinical efficacy. It appears from the early studies of the drug Donepezil that it was estimated that 80% would achieve optimal therapeutic serum levels at the standard dosage of 10 mg per day (3,4,5). Correspondingly, a dose-response relationship was found for the other ChEIs (rivastigmine, galantamine) and the partial glutamate receptor antagonist memantine (Ebixa), which is reserved for patients with moderate to severe AD or LBD, and a recommended dosage was established with a view to optimal clinical response (6). The indicative serum ranges are 80-200 nmol/l and 500-840 nmol/l for donepezil and memantine respectively (7). There have been remarkably few following studies investigating whether serum concentrations in a clinical setting are actually within the therapeutic reference ranges of the current recommendations. A recently published study suggests that very few patients in fact do reach a serum concentration within the recommended therapeutic reference ranges on the standard dosage (8). At the same time, few researchers have previously taken an interest in whether the occurrence of early side effects, possibly on a low dosage, and/or clinical need for repeated adjustments in drug dosing or alternatively change of preparation, could be due to abnormally high serum concentrations of the drug. Possibly reason for this could be genetic variation, sex differences, co-morbidity, compliance problems or drug interactions (9,10). For the planned research study conducted according to this protocol, we will initially focus on the two most widely used anti-dementia drugs, Donepezil and

Memantine, because an estimated 80% of patients who are treated with anti-dementia drugs are on one of these 2 drugs.

A pilot study carried out in collaboration between RVD and [The Laboratory of] Filadelfia showed that out of 24 blood samples, all taken from patients treated with donepezil at steady-state, only 8 samples, i.e. corresponding to 1/3, were within in the recommended therapeutic reference range. Ten samples were below the lower recommended limit, while 6 samples were above.

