- Approx. 30 patients will have a standard EEG with modified photo-block performed, if Donepezil treatment has not been started beforehand. These approx. 30 patients will have another standard EEG performed with the same modified photo-block approx. one year later in connection with the point below.
- After one year, all participants are called for one additional visit. Here, a blood test is carried out on all participants, just as all participants are offered a dosage adjustment depending on the serum concentration, also if appropriate a change of preparation. The same clinical tests are carried out as during the preliminary examination [or enrollment visit]. All participants are asked about treatment compliance.

- If there is a need for dose adjustment or possibly prescription change during the project, the decision will be made by the person in charge of the experiment [primary investigator] and not the project manager (PhD student). Practical handling is carried out in collaboration between the project manager and the project nurse.
- A blinded calculation of the distribution of serum concentration, clinical scores, compliance and occurrence of side effects [is done by a statistician not affiliated with the study]

Study visits

- In connection with the information interview, as part of the general clinical course, the initial information about the project is provided and project information is provided.
- Potential participants are contacted to participate in one extra visit (inclusion interview with project manager) together with the relative.
- If informed consent is obtained, one extra visit to the clinic 1 year after enrollment ["1 year follow-up visit"]. The visit ½ year after enrollment is part of the routine follow-up at RVD.

End of study

The study is ended on the date when the last participant (cf. power calculation) has been evaluated at the 1-year follow-up visit. Subsequently, after registration and [external] monitoring [of data quality], data will be transferred to blinded statistical analysis by a statistician. A need for future follow-up visits will be conducted at the GPs office.

Study design

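### The 80% power needs 55 evaluable participants per arm; the plan makes this 110 to be included, with no allowance for loss, so the figure holds only if nobody is lost

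*Combined protocol and SAP*

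**What the plan says.** The section Statistics and power calculation uses a formula for two independent proportions with a two-sided 5% level and 80% power. For the control arm it reads: "If it is assumed that <50% of the participants reach the recommended serum concentration and thus relevant clinical effect on standard dosing". For the intervention arm it assumes that "this can be increased to 75% by dose adjustment after S concentration determination". The values entered are 0.50 and 0.75, the result is about 55 per group, and the conclusion is that "110 participants must be included in the project period in order to calculate the clinical utility of serum concentration measurements", under the stated assumptions. The same section defines success as an MMSE fall of less than 2 points over one year, so each participant needs a one-year score to be classified.

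The section Withdrawal criteria for all covers participants who wish to leave or whose relative wishes it, those with symptoms judged unacceptable, and "Medical reasons, including if the treatment is changed to an anti-dementia drug for which serum concentrations are not measured in this study" (galantamine or rivastigmine). The protocol gives no expected rate of loss, inflation factor, replacement rule, analysis set or missing-data rule.

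The enrolment figure is not the same throughout. The power section gives 110. The Randomization section speaks of 150 project numbers but numbers them 1 to 110. The lay summary (Recruitment) gives about 100. The End of study section states: "The study is ended on the date when the last participant (cf. power calculation) has been evaluated at the 1-year follow-up visit".

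**The concern.** The N in the formula is the number per arm whose outcome enters the comparison. The plan uses it as the number to be included. The two are equal only if every participant has a one-year MMSE score and stays in the analysis. Follow-up lasts a year, the participants have dementia, and the protocol foresees withdrawal, so some loss should be planned for.

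The 80% is the only power figure the protocol states. If participants are lost from 110, that figure is too high under the plan's own assumptions, and a null result could be read as stronger evidence against benefit than the data support.

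**Working it through.** **Inputs** (Statistics and power calculation): z = 1.96 for the two-sided 5% level; z = 0.84 for 80% power; P1 = 0.50; P2 = 0.75. The loss rates below are assumptions.

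**Step 1. Reproduce the plan's figure.**
N > (1.96 + 0.84)² × (0.50 × 0.50 + 0.75 × 0.25) / 0.25² = 7.84 × 0.4375 / 0.0625 = 54.88, so 55 per arm and 110 in total. This agrees with the plan.

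**Step 2. Turn the same formula round to give power.**
Power = Φ(|P1 − P2| / √[(P1(1 − P1) + P2(1 − P2)) / n] − 1.96) = Φ(0.25 / √(0.4375 / n) − 1.96)

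At n = 55: 0.25 / √(0.4375 / 55) = 0.25 / 0.0892 = 2.803; 2.803 − 1.96 = 0.843; Φ(0.843) = 80.0%. There is no margin.

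**Step 3. Apply loss to 110 enrolled, 55 per arm.**

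| Evaluable per arm | Loss | 0.25 / √(0.4375 / n) | Power |
|---|---|---|---|
| 55 | none | 2.803 | 80.0% |
| 50 | about 10% | 2.673 | 76.2% |
| 44 | 20% | 2.507 | 70.8% |
| 38 | about 30% | 2.330 | 64.4% |

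A 5% loss (52.25 per arm on average) gives 78.0%.

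**Step 4. Vary the enrolment total.**
- With 100 enrolled (50 per arm), power is 76.2% before any loss.
- With 150 enrolled, 110 remain evaluable up to a loss of 1 − 110/150 = 26.7%.

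**Step 5. Vary the control rate, keeping P2 at 0.75.** The plan says below 50% but enters 0.50.
- P1 = 0.48, 50 per arm: 82%.
- P1 = 0.47, 44 per arm: 80%.
- P1 = 0.45, 38 per arm: 80%; with 55 per arm, 92%.

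**Step 6. Count lost participants as failures instead of excluding them.** Both success rates then shrink by the loss fraction. At 10% loss they become 0.45 and 0.675 with 55 per arm. The pooled-variance version of the calculation gives 66.6%, against 78.1% on that version with no loss. Keeping withdrawn participants in the analysis this way does not restore the power.

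**The case against.** The strongest case on the other side has four parts.

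**The enrolment total is not settled.** A reader might infer that the trial enrols exactly 110. The documents do not establish this. They also give 150 and about 100, and the End of study wording can be read as 110 evaluated. The Time schedule reports extended recruitment, closed on 24 February 2022, without a final number. This stands, and the power figures for 110 are therefore conditional. It does not show a reserve either: the 150 is contradicted within its own sentence and is nowhere described as an allowance for loss, while the power section speaks of inclusion and calls the number a recruitment goal.

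**The control rate is the conservative end.** A reader might also infer that the design cannot reach 80%. That does not follow, because the plan assumes a control rate below 50% and computes at the boundary. A slightly lower rate with P2 held at 0.75 makes up for the loss (Step 5). This stands as a limit on the conclusion. The pilot does not turn it into evidence of spare power: "only 8 samples, i.e. corresponding to 1/3, were within in the recommended therapeutic reference range" is a serum-range rate in donepezil-treated patients, not a rate of MMSE response.

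**No loss rate is documented.** True. The Background states that an estimated 80% of treated patients use donepezil or memantine. It would be tempting to read a switching risk into this, but it is a share of drug use and says nothing about loss after enrolment. The section Side Effects and Adverse Events describes a switch of drug as common practice when side effects are judged drug-related, but gives no rate. A switch between donepezil and memantine is not withdrawal under the listed criterion.

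**Choice of test.** Fisher's exact test would give lower power still: 67.5% at 50 per arm and 61.1% at 44. Its value with no loss is already 72.1%, so most of the gap from 80% at 50 per arm comes from the test. The documents name no test, and the point does not rest on these figures.

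**Conclusion.** The sample-size arithmetic is correct. The step from 55 needed per arm to 110 included is wrong as written, because the stated power then holds only with zero loss. At 0.50 versus 0.75 with 110 enrolled in equal arms, power is about 76%, 71% and 64% at assumed losses of about 10%, 20% and 30%. A 5% loss costs about 2 percentage points.

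The conclusion rests on three conditions: 110 is the enrolment total, the control rate is 0.50, and lost participants are excluded from the analysis. The documents do not show that the trial is underpowered. They show that its only power statement lacks the condition on which it depends.

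**What to change.** No further enrolment is proposed; recruitment has closed.

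1. In Statistics and power calculation, restate the conclusion along these lines: *80% power requires 55 evaluable participants per arm at 0.50 versus 0.75; with 110 enrolled, power is about 76%, 71% and 64% at 10%, 20% and 30% loss.* Mark the loss rates as assumptions.
2. Reconcile the three enrolment figures: about 100 (lay summary, Recruitment), 110 (power section) and 150 numbered 1 to 110 (Randomization).
3. Before unblinding, define the analysis set and how participants without a one-year MMSE score are handled.
4. In the report, give the numbers enrolled and evaluable at 12 months per arm, with a confidence interval for the difference in proportions. Do not report post-hoc power; the interval shows directly what a null result can exclude.

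The cost is a few sentences and a less favourable power statement. No trial procedure changes.
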